3.2 Scientific Rationale for Study Design

The current study is part of a two-phase project.

- Phase 1 (the current study) is an analytical study to validate and expand upon the Xpert MTB/XDR analytical data that the manufacturer (Cepheid, Sunnyvale, California) has compiled for internal validation, CE-IVD marking and/or other regulatory purposes.
- Phase 2 is a clinical study to determine the diagnostic accuracy at intended settings of use.

The two phases will provide complementary pieces of evidence to address the study objectives.

The main purpose of this clinical study is to confirm accuracy estimates from the external laboratory validation and ensure that Xpert MTB/XDR diagnostic performance characteristics will be consistent at sites of intended use. Assay performance when testing sputum samples (direct testing) and cultured isolates (indirect testing), assay performance compared to the Hain MTBDR*plus* and MTBDRs/ (Hain Lifesciences GmbH) line probe assays (LPAs), and assay error and failure rates and device operational characteristics will also be assessed during this phase of the study.

In order to address clinical study objectives quickly and efficiently, this study will first assess Xpert MTB/XDR performance for Xpert MTB/RIF MTB-positive samples from patients prospectively enrolled in the study. Focusing the study on Xpert MTB/RIF MTB-positive samples is in line with the intended use of the assay as a reflex, or follow-up, test to any Xpert MTB/RIF or Ultra MTB-positive result. This will also allow for an assessment of assay performance for INH resistance detection among all MTB-positive samples including INH mono-resistant, as this population might be different from a largely RIF-resistant population. However, to ensure numbers are adequate for an assessment of Xpert MTB/XDR assay performance for second-line resistance detection, once sufficient MTB-positive, RIF-sensitive samples have been tested, a subset of solely Xpert RIF-resistant samples will be tested until enrolment targets are met (see section 9.1 and Appendix 4: Sample Requirement to Achieve Target Sample Size).

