3.4 End of Study Definition

Phase II will be considered completed once all *in vitro* diagnostic (IVD) testing has completed and all culture, DST and NGS results have been returned for at least 284 TB-positive and 316 additional RIF-resistant clinical samples, and all user appraisal questionnaires have been completed at the three clinical sites.

4 Study Population and Eligibility

Individuals who have one or more risk factors for DR-TB presenting to participating centres will be screened by Xpert MTB/RIF or Ultra. Those who test MTB-positive by Xpert MTB/RIF or Ultra at the study sites will be asked to participate. Once at least 360 MTB-positive patients have been tested, an additional subset of Xpert MTB-positive, RIF-resistant patients (n=400) will also be asked to participate in this study. Individuals will be recruited at outpatient clinic settings and inpatient hospital settings. Individuals will be asked by non-study clinicians or staff if they would be interested in participating in the study. Interested individuals will be referred to study personnel for additional information and screening, if appropriate. HIV-positive individuals and HIV-negative individuals will be included in this study.

Prospective approval of protocol deviations to recruitment and enrolment criteria, also known as protocol waivers or exemptions, is not permitted.

4.1 Inclusion Criteria:

Patients meeting the following criteria will be screened by Xpert MTB/RIF or Xpert MTB/RIF Ultra:

- Age 18 years or above;
- Symptoms suggesting pulmonary TB, i.e. persistent cough (generally ≥ 3 weeks or as per local definition of TB suspect), **and** at least one of the following:
 - Previously received >1 month of treatment for a prior TB episode **or**
 - Failing TB treatment with positive sputum smear or culture after ≥ 3 months of a standard TB treatment **or**
 - Had close contact with a known drug-resistant TB case **or**
 - Newly diagnosed with MDR-TB within the last 30 days **or**
 - Previously diagnosed with MDR-TB and failed TB treatment with positive sputum smear or culture after ≥ 3 months of a standard MDR-TB treatment regimen

Patients meeting the above criteria will be screened by Xpert MTB/RIF or Xpert MTB/RIF Ultra. TB patients meeting the following criteria will be included in the study:

- A clear Mtb-positive and RIF-resistant or RIF-sensitive result by Xpert MTB/RIF or Xpert MTB/RIF Ultra
- Provision of informed consent;

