6.1.1 Sample Selection

Up to two sputum samples ($\geq 3\text{mL}$) will be collected from consecutive, prospectively-enrolled patients with defined risk factors for DR-TB and a valid Xpert MTB/RIF or Xpert MTB/RIF Ultra result. Depending upon enrolment rates, study timelines may be accelerated by also using existing, well-characterized frozen TB clinical (sputum) samples collected during the course of routine clinical care and TB surveillance in the sites of intended use. These samples will only be used if recruitment or enrolment is slow at one or more sites. At the 4-week study time point, recruitment rates will be assessed to determine whether this use of additional samples will be necessary.

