6.1.2 Study Workflow

Study flow is shown in Figure 1. All available Xpert MTB/RIF TB-positive samples will be tested in this study (i.e. consecutive patient samples) until sample size targets are met. All molecular assays will be performed in accordance with SOPs provided by the manufacturers. Specimen handling and processing by routine tests will be carried out according to NTP local policies and standards.

Samples will first be tested by Xpert MTB/RIF or Ultra, as part of routine diagnostic procedures. This Xpert MTB/RIF step will act as a screening tool for trial enrolment. Participants testing positive for MTB by Xpert MTB/RIF will be asked to volunteer for the Xpert MTB/XDR trial. This (testing of specimens from TB-positive samples) is in line with the intended use of the XDR assay as an add-on test to the Xpert MTB/RIF assay.

[figure not shown]
A staged enrolment will proceed: Stage 1 will enrol 360 MTB-positive participants, irrespective of RIF resistance/sensitivity. Once enrolment is complete, Stage 2 will enrol 400 MTB-positive RIF-resistant participants (see section 9.1 and Appendix 4: Sample Requirement to Achieve Target Sample Size). This staging is designed to better evaluate Xpert MTB/XDR sensitivity for second-line resistance detection.

In order to efficiently assess the diagnostic performance of the Xpert MTB/XDR assay, participants will be asked to provide ≥ 3 ml of sputum (either a single sputum or two consecutively collected and pooled sputa). Samples will be homogenized and split for testing.

The Xpert MTB/XDR assay and acid-fast bacilli smear will be performed on the direct sample. 2ml of sputum will be decontaminated and used for MGIT and LJ culture.

Following direct testing, phenotypic MGIT DST will be performed for all culture-positive samples for INH, RIF, fluoroquinolone (moxifloxacin and levofloxacin), AMK, ETH (ethionamide), KAN and CAP. Cultured samples will also undergo subsequent molecular testing by LPA and targeted NGS of relevant gene regions (*katG*, *inhA*, *fabG1*, *ahpC*, *gyrA*, *gyrB*, *rrs*, and *eis*) and another Xpert MTB/XDR assay. NGS will be performed from the culture isolate to obtain sequencing reads of high quality.

Figure 1. Phase II sample flow

≥ 3ml of sputum is required for the trial. This can be achieved through an individual sputum or pooling of serially collected sputa, homogenized with glass beads.

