Appendix 4: Sample Requirement to Achieve Target Sample Size

	MTB+ group*		Additional RIF-R group		TOTAL
Samples Tested	100%	360	100%	400	760
Invalid Xpert Ultra results	1%	4	1%	4	8
Culture-contaminated	10%	36	10%	40	76
Molecular-test non-determinant*	10%	36	10%	40	76
Included**	79%	284	79%	316	600
INH-resistant	29%	82	99%	313	395
INH-sensitive	71%	202	1%	3	205
FQ-resistant	5%	14	25%	79	93
FQ-sensitive	95%	270	75%	237	507
AMK/CAP-resistant	2%	6	9%	28	34
AMK/CAP-sensitive	98%	278	91%	288	566
KAN-resistant	1%	3	21.5%	68	71
KAN-sensitive	99%	281	78.5%	248	529

*Assume 23% of TB-positive samples are RIF-R based upon previous studies and data from these regions^{11,13}.

**We assume 29% INH resistance, 5% FQ resistance and 1-2% second-line injectable (AMK, KAN and CAP) resistance among TB-positive patients based upon previous studies and data from these regions^{11,13}. Testing 284 TB-positive specimens (based on Xpert MTB/RIF and Ultra-testing) would then be expected to yield 82 INH-resistant but only 14 FQ-resistant specimens and 3-6 second-line injectable-resistant specimens (limiting factor in sample size calculations). This allows for determination of Xpert MTB/XDR performance for INH resistance detection as a reflex test to any TB-positive result, but is not sufficient for determination of Xpert MTB/XDR performance for second-line resistance detection. To efficiently get to a sufficient number of second-line resistant samples, we will supplement this by testing 316 additional RIF-resistant samples. To account for contaminated cultures and invalid/non-determinant Xpert MTB/RIF or Ultra, NGS and Xpert MTB/XDR results, we would inflate these numbers by 21%, leading to a total of 360 TB-positive and 400 additional RIF-resistant samples, i.e. a total of 760 patient samples tested in this study.

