The results will serve as an early indicator of Xpert MTB/XDR accuracy in the clinical trial. If performance estimates fall outside of the presented confidence intervals for resistance detection (Table 2), the Data Monitoring Committee (DMC) will review all data for accuracy and consistency. Additionally, the sponsor may conduct a monitoring visit to one or more sites to ensure adherence to SOPs and effective data management.

7 Additional sub-group analyses

Subgroups analyses, and definitions of subgroups, are described in section 4.3. No additional subgroup analyses will be performed.

8 Multiple comparisons/multiplicity adjustments

No multiple testing of statistical hypotheses is going to be performed.

9 Exploratory analyses

No exploratory analyses will be performed.

10 Sample size

To achieve the targeted precision for accuracy estimates, it is estimated that 760 samples will need to be tested for this study, with a final 284 MTB-positive and an additional 316 RIF-resistant samples tested by Xpert MTB/XDR and all reference standards and comparators, i.e. a total of 600 specimen results available for analysis. The desired precision for the accuracy estimates was chosen to achieve high confidence in the estimates for Xpert MTB/XDR resistance detection when considering evidence from both the 'external laboratory validation' (phase I) and the clinical trial (phase II). The sample size is detailed below in Table 2.

		n	Point estimate (95%CI) *	Total width of CI *
INH	Sensitivity	395	90% (86, 93)	7%
	Specificity	205	98% (95, 99)	4%
FQs	Sensitivity	93	90% (82, 95)	13%
	Specificity	507	98% (96, 99)	3%
AMK	Sensitivity	34	90% (74, 97)	23%
	Specificity	566	98% (96, 99)	3%
KAN	Sensitivity	71	90% (80, 96)	16%
	Specificity	529	98% (96, 99)	3%
CAP	Sensitivity	34	90% (74, 97)	23%
	Specificity	566	98% (96, 99)	3%

Table 2 Sample size

* 95%CI based on Wilson's score method (as recommended by Newcombe et al. as well as CLSI/FDA) using continuity correction.

11 Minimization of error and bias

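### Stage 1 is justified as measuring INH detection in any TB-positive patient, but no final analysis in the SAP reports INH accuracy for Stage 1 or by RIF result

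*SAP*

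**What the plan says.** Protocol 3.2 gives the reason for starting with unselected MTB-positive patients: "This will also allow for an assessment of assay performance for INH resistance detection among all MTB-positive samples including INH mono-resistant", because "this population might be different from a largely RIF-resistant population". Appendix 4 says of the 284 Stage 1 specimens: "This allows for determination of Xpert MTB/XDR performance for INH resistance detection as a reflex test to any TB-positive result". Protocol 6.1.2 fixes the enrolment: "Stage 1 will enrol 360 MTB-positive participants, irrespective of RIF resistance/sensitivity". Stage 2 then takes RIF-resistant patients only (400 tested, 316 evaluable).

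SAP 4.2 evaluates INH accuracy once, on the per-protocol set, which SAP 3.2 defines without regard to stage. SAP 4.3 splits results by specimen type, site, smear grade, gene target, Hain comparator, HIV status, previous treatment, and screening assay (Ultra or MTB/RIF). SAP 7 refers back to that list and adds "No additional subgroup analyses will be performed"; SAP 9 rules out exploratory analyses.

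**The concern.** The protocol names a target population for INH detection and gives a reason not to rely on RIF-resistant patients for it. The SAP then reports a single INH sensitivity in which RIF-resistant patients dominate.

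The reflex-test item in SAP 4.3 looks as if it fills the gap but does not. It separates patients by which assay was used for screening, not by what that assay found. The gene-target counts and smear tables are only indirect checks. The first interim look (200 samples) should fall within Stage 1, since 360 are enrolled there first. But it compares with NGS alone, not the composite standard, and serves as a data check.

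Pooling distorts sensitivity only if sensitivity differs by RIF status. The documents do not show that it does, but the protocol raises the possibility. Under the SAP as written, a reader who wants INH performance after any TB-positive screening result would have no planned estimate to look up.

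**Working it through.** **1. The plan's own figures (Appendix 4 and Table 2).**

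- INH-resistant: 0.29 × 284 ≈ 82 in Stage 1 and 0.99 × 316 ≈ 313 in Stage 2, total 395.
- INH-sensitive: 202 + 3 = 205.

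Table 2 uses the 95% Wilson interval with continuity correction. With q = 1 − p and z = 1.96:

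lower = [2np + z² − 1 − z√(z² − 2 − 1/n + 4p(nq + 1))] / [2(n + z²)]

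upper = [2np + z² + 1 + z√(z² + 2 − 1/n + 4p(nq − 1))] / [2(n + z²)]

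At p = 0.90, n = 395 this gives 86.5 to 92.7. At p = 0.98, n = 205 it gives about 94.7 to 99.3. Both match Table 2 after rounding. The printed widths of 7 and 4 are differences of rounded limits; unrounded they are 6.2 and 4.7 points.

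**2. Share of each stage.** Stage 2 supplies 313/395 = 79.2% of the sensitivity denominator and Stage 1 supplies 82/395 = 20.8%. For specificity, Stage 1 supplies 202/205 = 98.5%, so the pooled specificity is nearly the Stage 1 specificity already.

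**3. Share of RIF-sensitive patients.** Appendix 4 states: "Assume 23% of TB-positive samples are RIF-R based upon previous studies and data from these regions". That gives 0.23 × 284 = 65.3 RIF-resistant patients in Stage 1. The documents do not say how many of these are INH-resistant, so let that fraction be r and vary it. The RIF-sensitive, INH-resistant count is 82 − 65.3r. Dividing it by 395 gives its weight in the pooled sensitivity; dividing by 82 gives its weight in Stage 1. The last two columns multiply those weights by a hypothetical 10-point shortfall in sensitivity among RIF-sensitive patients.

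| r (assumed) | RIF-sensitive, INH-resistant | Weight, pooled | Weight, Stage 1 | Shift, pooled (points) | Shift, Stage 1 (points) |
|---|---|---|---|---|---|
| 0.80 | 29.7 | 7.5% | 36.3% | 0.75 | 3.6 |
| 0.90 | 23.2 | 5.9% | 28.3% | 0.59 | 2.8 |
| 0.99 | 17.3 | 4.4% | 21.1% | 0.44 | 2.1 |
| 1.00 | 16.7 | 4.2% | 20.3% | 0.42 | 2.0 |

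A deliberately large example, with assumed sensitivities of 92% in RIF-resistant and 60% in RIF-sensitive patients and r = 0.99:

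- Pooled: (0.92 × 377.7 + 0.60 × 17.3)/395 = 90.6%, inside Table 2's interval of 86 to 93.
- Stage 1: (0.92 × 64.7 + 0.60 × 17.3)/82 = 85.2%.

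**4. How far to trust the counts.** Appendix 4's rows do not combine exactly in this way. For KAN, 0.23 × 0.215 × 284 = 14.0, against 3 stated. The range of about 17 to 30 is therefore approximate. The 79% share by stage does not depend on it.

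**5. Precision of the missing rows (same interval method).**

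| Row | n | Assumed value | 95% CI |
|---|---|---|---|
| Stage 1 INH sensitivity | 82 | 90% | 80.9 to 95.2 |
| Stage 1 INH specificity | 202 | 98% | about 95 to 99 |
| RIF-sensitive, INH sensitivity (low count) | 17 | 90% | 64.3 to 98.6 |
| RIF-sensitive, INH sensitivity (high count) | 30 | 90% | 72.3 to 97.4 |

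**The case against.** The strongest reply is that no formal objective or endpoint calls for a Stage 1 estimate. Objective 1.1 lists the 284 and the 316 together, Table 2 sets INH precision on 395, and Protocol 9.2 has all samples with both results contribute. On this reading the SAP implements the objectives, and 3.2 and Appendix 4 are only rationale. It is also fair that a 0.4 to 0.8 point shift is small against a pooled interval 6.2 points wide, and that the RIF-sensitive row would be too thin to settle anything.

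Part of this stands. The Stage 1 estimate is a stated rationale, not a listed endpoint, and the pooled estimate is legitimate as primary. But the small pooled shift is the problem itself: the pooled figure cannot register a difference that the protocol thought worth designing for. Low precision is no reason to omit the Stage 1 row either. Its width of about 14 points sits beside 13 (FQ), 16 (KAN) and 23 (AMK and CAP) accepted in Table 2, and Appendix 4 treats the 82 samples as enough for this purpose. The split by RIF result has its own support, since Protocol 5.3.1 announces sub-groups by drug-resistance profile and the SAP has none.

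Two further cautions are fair but do not remove the gap. Protocol 3.2 describes the switch to Stage 2 as following enough RIF-sensitive samples, while 6.1.2 fixes it at 360 patients; the label on a Stage 1 row depends on which was followed. And SAP Table 3 counts either phenotypic or NGS resistance as resistant while Table 4 requires both, so 82 and 395 could shrink under Table 4.

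**Conclusion.** The concern holds. Following the SAP exactly would leave a stated purpose of the two-stage design unreported: no final analysis against the composite standard gives INH accuracy in Stage 1 or by RIF result. The consequence is confined to INH sensitivity, where 79% of the planned denominator is from Stage 2. Including the RIF-resistant patients of Stage 1, 92-96% is RIF-resistant if 80-100% of those patients are INH-resistant. Nothing here shows that sensitivity does differ by RIF status, and the primary estimate need not change. This is an inexpensive improvement that should be made before database lock, because adding it afterwards would be post hoc and contrary to SAP 7 and 9. The omission is certain; the RIF-sensitive counts are approximate.

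**What to change.** Keep the pooled primary estimate. Add to SAP 4.3, for INH only:

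1. Sensitivity and specificity with 95% Wilson intervals in Stage 1 alone. Label it as the estimate for MTB-positive patients with at least one DR-TB risk factor, irrespective of RIF result, because Protocol section 4 limits screening in that way: "Individuals who have one or more risk factors for DR-TB presenting to participating centres will be screened by Xpert MTB/RIF or Ultra".
2. A descriptive split of INH sensitivity by screening Xpert RIF result, flagged as imprecise.

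Footnote how many Stage 1 samples, if any, were frozen. Protocol 6.1.1 permits them conditionally: "These samples will only be used if recruitment or enrolment is slow at one or more sites". Amend SAP 7 so that these rows are allowed.

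The cost is a few table rows with no new patients or testing. Protocol 11.2 has Xpert results transcribed into the CRF, but neither document mentions recording the enrolment stage, so confirm that it is in the analysis dataset. The downside is wider intervals, as shown above. The new rows report the estimate the protocol describes; they cannot show or rule out a modest difference by RIF status, and the table should say so.

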11.1 Enrolment and randomization procedures

Describe how enrolment will be carried out (from the clinical protocol) and add details on the randomization procedure (if applicable)

12 Case definitions

Table 3 describes the categorization of results based on test results.

TEST RESULT	DESCRIPTION
Phenotypic Drug*-resistant	Culture-positive and growth for Drug* in conventional DST testing.
Phenotypic Drug*-sensitive	Culture-positive and no growth for Drug* in conventional DST testing
Genotypic Drug*-resistant	NGS identifies mutations recognized to be associated with resistance (defined based on consultation with WHO prior to analysis)
Genotypic Drug*-sensitive	NGS identifies no mutations recognized to be associated with resistance (defined based on consultation with WHO prior to analysis)
Composite reference standard Drug*-resistant	If Phenotypic Drug*-sensitive but NGS identifies mutations recognized to be associated with Drug* resistance for the respective gene regions, the composite reference standard will be considered Drug*-resistant. If Phenotypic Drug*-resistant but NGS does not identify mutations recognized to be associated with Drug* resistance for the respective gene regions, the composite reference standard will be considered Drug*-resistant (as mutations will be assumed outside of the region sequenced).
Composite reference standard Drug*-sensitive	If Phenotypic Drug*-sensitive and NGS shows either no mutations or only mutations that are not associated with Drug* resistance for the respective gene regions.

* Drug: INH, ETH, FQ (moxifloxacin and levofloxacin for phenotypic DST), AMK, KAN or CAP

Table 3 Case definitions

13 Statistical software

The analysis will be performed using the R statistical language (version 3.4.0 or higher) on OsX, and Microsoft Excel 2018 (version 16.16 or higher).

14 References

Add required references.

15 Document history

Version	Notes / Changes
1.0	Initial version

16 Appendix

The definitions of composite reference standards are given in table 4.

DRUG RESISTANCE	COMPOSITE REFERENCE STANDARD
INH-resistant	NGS of katG , fabG1 , ahpC and inhA detects ≥ 1 mutation associated with INH resistance and MGIT culture is INH drug-resistant at the critical concentration.
ETH-resistant	NGS of inhA detects ≥ 1 mutation associated with ETH resistance and MGIT culture is ETH drug-resistant at the critical concentration.
FQ-resistant	NGS of gyrA and gyrB detects ≥ 1 mutation associated with MFX resistance and MGIT culture is MFX drug-resistant at the critical concentration.
AMK-resistant	NGS of rrs and eis detects ≥ 1 mutation associated with AMK resistance and MGIT culture is AMK drug-resistant at the critical concentration.
KAN-resistant	NGS of rrs and eis detects ≥ 1 mutation associated with KAN resistance and MGIT culture is KAN drug-resistant at the critical concentration.
CAP-resistant	NGS of rrs detects ≥ 1 mutation associated with CAP resistance and MGIT culture is CAP drug-resistant at the critical concentration.
INH-susceptible	NGS of katG , fabG1 , ahpC and inhA does NOT detect any mutation associated with INH resistance and MGIT culture is INH-susceptible at the critical concentration.
ETH-susceptible	NGS of inhA does NOT detect any mutation associated with ETH resistance and MGIT culture is ETH-susceptible at the critical concentration.
FQ-susceptible	NGS of gyrA and gyrB does NOT detect any mutation associated with MFX resistance and MGIT culture is MFX-susceptible at the critical concentration.
AMK-susceptible	NGS of rrs and eis does NOT detect any mutation associated with AMK resistance and MGIT culture is AMK-susceptible at the critical concentration.
KAN-susceptible	NGS of rrs and eis does NOT detect any mutation associated with KAN resistance and MGIT culture is KAN-susceptible at the critical concentration.
CAP-susceptible	NGS of rrs does NOT detect any mutation associated with CAP resistance and MGIT culture is CAP-susceptible at the critical concentration.

Table 4 Definition of composite reference standards
